	6.5 Intervention	
	6.6 Procedures	11
	6.6.1 Subject Eligibility assessment 6.6.2 Randomization	.11
	6.6.3 Allocation concealment and blinding	.11
	6.6.4 Communication with Receiving Ward Staffs	.12
	6.6.6 Procedure	.12
	6.6.7 Microbiological assessment	13
7	6.6.8 Follow up	13 14
7. 8	Assessment of Safety	11
ο. α	Statistics and Data Analysis	11
J. 40	Outcomes and massures	
10.	Direct Access to Source Date/ Decuments	
11.	Direct Access to Source Data/ Documents	
12.	Ethics	
13.	Data Handling and Record Keeping	16
14.	Financing and Insurance	16
15.	Publication Policy	17
16.	References	18
Appendix '	l	20
Appendix 2	2	21
Appendix 3	3	22
Appendix 4	4	23
Appendix &	5	24
Appendix (5	25
Appendix 7	7	26
Appendix 8	3	27

1. List of Abbreviations

AE	Adverse event
A&E	Accident and Emergency
AECOPD	Acute Exacerbation of Chronic Obstructive Pulmonary Disease
AIDS	Acquired immunodeficiency syndrome
BA	blood agar
CCQ	Clinical COPD Questionnaire (Appendix 1)
CI	Confidence Interval
COPD	Chronic obstructive pulmonary disease
CONSORT	Consolidated Standards of Reporting Trials
CRP	C-reactive protein
CRQ-SAS	Chronic Respiratory Disease Questionnaire, self-administered, standardized (Appendix 2)
ED	Emergency Department
EQ-5D	EuroQoL 5-dimension
EQ-5D-5L	EuroQoL 5-dimension 5-level (Appendix 3)
GOLD	Global Initiative for Chronic Obstructive Lung Disease
HA	Hospital Authority
HOKLAS	Hong Kong Laboratory Accreditation Scheme
ICU	Intensive Care Unit
IQR	Interquartile range
ISO	International Organization for Standardization
ITT	Intention-to-treat
MALDI-ToF-MS	Matrix Assisted Laser Desorption Ionising Time of Flight Mass Spectrometry
NEWS2	National Early Warning Score 2
PCT	Procalcitonin
OR	Odds ratio
QALY	Quality-adjusted life year
QMH	Queen Mary Hospital
RCT	Randomized Controlled Trial
RT-PCR	Reverse transcription polymerase chain reaction
SAE	Serious adverse event
UTI	Urinary Tract Infection

2. Study Summary

Title	Antibiotic stewardship through CRP-guided antibiotic treatment for patients with Acute Exacerbation of Chronic Obstructive Pulmonary Disease (AECOPD)					
Short Title	Antibiotic stewardship in AECOPD					
Protocol Number	AECOPD-[name]-21200182					
Methodology	Patient-level, multi-centre, single-blind, open-label, randomized, combined superiority (antibiotic duration) and non-inferiority (COPD health status) trial.					
Study Duration	36 months					
Study Centre	Multiple centres					
Objectives	To determine whether the addition of serial CRP levels (with advice on interpretation) to usual care for managing AECOPD leads to a reduction in antibiotic exposure (defined as the total number of antibiotic days by Day 28) for AECOPD without negatively impacting on COPD health status, compared with usual care alone					
Number of Subjects	N=1,184					
Diagnosis and Main Inclusion Criteria	 Being diagnosed with active AECOPD; AND Known COPD in their medical records; AND Age 40 years or older; AND Able to provide informed consent in Cantonese, Mandarin, or English; AND Able to complete the questionnaires during the study period 					
Participation						
Duration	One year					
Interventions	The intervention group will be recommended to test for CRP at randomization and every day during the stay. Antibiotics are considered for discontinuation when CRP reduces below 5mg/dL, on top of existing clinical judgment. The control group will not be tested for CRP and antibiotics will be discontinued according to clinical judgment.					
Main outcome measures and study instruments	The antibiotic exposure (total number of antibiotic days) and recovery in terms of COPD health status (Clinical COPD Questionnaire total scores) within 28 days from randomization. The secondary outcomes include prevalence of potentially pathogenic bacteria and commensal organisms and their proportion of drug-resistant strain, antibiotics prescribed and total antibiotics consumption (doses), adverse effects potentially attributable to antibiotics prescribed for the exacerbation, general health status, disease-specific, health-related quality of life over time measured using the CRQ-SAS (dyspnoea, fatigue, emotion function, mastery and total scores) and costs (total HA cost) and cost-effectiveness.					
Statistical Methodology	 Baseline subject characteristics: descriptive statistics. COPD-related health status, general health status, and duration of antibiotics: Fisher exact tests. Adverse effects and number of events: Chi squared tests. Between-group difference, CCQ score, and EQ-5D: Students' t-test. Group comparison for categorical variables: Fisher 's Exact test All analyses will be performed using Stata software For missing data handling: multiple imputation methods. Cost evaluations: the healthcare provider using standard methods. Cost-effectiveness analysis during the RCT: ITT principle. Health economic outcomes: QALY. 					

4 of 27 31st Oct 2021 1.1

3. Investigators

CRP-guided antibiotic prescription is effective and safe. In hospitalised AECOPD patients with CRP-guided prescriptions (antibiotic treatment if CRP \geq 50 mg/L, i.e. 5mg/dL) versus a control group with standard GOLD treatment fewer patients in the CRP group were prescribed with antibiotics compared to the GOLD group (31.7% versus 46.2%, p=0.028; adjusted odds ratio (OR) 0.178, 95% CI 0.077–0.411, p=0.029), without a significant difference in the treatment effects between both groups. Yet, the discontinuation of antibiotics in both groups was guided by clinical judgment. The 30-day treatment failure rate was nearly equal in CRP and control groups (44.5% vs. 45.5%, p=0.881), the time to next exacerbation was comparable (32 days vs. 28 days, p=0.713), and the length of hospital stay was also similar (7 days vs. 6 days, p=0.206). On day 30, there was no difference in the symptoms score and quality of life, and no serious adverse events were detected.

CRP-guided antibiotic discontinuation is also safe. Whether antibiotic therapy with CRPguided duration or fixed 7-day duration were clinically non-inferior to fixed 14-day duration in patients with uncomplicated gram-negative bacteraemia was determined in a multicentre trial involved 504 adults.¹⁵ The main outcome was the rate of clinical failure at 30 days, which was 2.4% in CRP-guided patients who experienced recurrent bacteraemia, local suppurative complications, distant complications, re-initiation of antibiotic therapy due to clinical deterioration, or any-cause mortality, compared with a failure rate of 6.6% in the 7-day group and 5.5% in the 14-day group. The CRP-guided treatment met the 10% margin for inferiority.

Work done by us

A&E is an ideal location to start antibiotic stewardship for AECOPD. Prior work has also been conducted by our team in Hong Kong to ensure the significance of the problem, the feasibility of data collection, and the preliminary results relevant to AECOPD patients with available CRP levels. 21,129 patients were admitted to emergency medicine wards and medical wards through A&E in 2019 (mean age 79 years (IQR 71-86)). Elevated CRP was associated with doubled odds ratio of ICU admission or death (Odds ratio 2.06, 95%CI 1.75 - 2.43). Analysis reveals that 96% of patients with a normal CRP were given antibiotics. Among those with normal CRP, unadjusted statistics suggested those without antibiotics did not have lower odds ratios for deterioration requiring ICU admission and for death (p<0.01) (Appendix 4, Table 1). Overall, AECOPD patients were prescribed antibiotics for a mean of 9.4 days (SD 10.3) but the mean duration of an elevated CRP was 6.4 days (SD 6.8). There is an opportunity to shorten antimicrobial regimen for some AECOPD patients. Further details of the results can be found in Appendix 4, Figure 1 and Figure 2. As personalised antibiotic treatments may reduce healthcare resource utilisation, we sought to determine the optimal antibiotics therapy duration for AECOPD patients based on clinical decision-making and CRP results.

Research Gaps

- 1. Antibiotic stewardship involves both appropriate prescription and timely discontinuation of an antibiotic treatment. Limited evidence informs antibiotic prescription practice for AECOPD in A&E. Information on CRP-guided antibiotic discontinuation is absent.
- 2. Previous studies with hospitalized AECOPD patients with severe symptoms and severe outcomes was insufficient in power.

3. Cost-effectiveness analyses on CRP-guided antibiotic treatment in AECOPD patients are lacking.

5. Aims and Objectives of the study

5.1 Clinical Question

In adult AECOPD patients in Emergency Departments, does CRP-guided antibiotic treatment, compared with usual care, lead to shorter antibiotic duration without negatively impact on clinical COPD-health status?

5.2 Aims and Hypotheses to be Tested:

This study seeks to establish whether serial CRP level guided clinical judgment can safely and cost-effectively be used to better target antibiotic treatment (include both treatment and discontinuation) for AECOPD in emergency departments to those that are most likely to benefit, so that overall antibiotic exposure duration is decreased without compromising COPD-related health status.

The **primary** objective is to determine whether the addition of a serial CRP levels to usual care for AECOPD leads to shorter antibiotic duration,

The **co-primary objective** is to determine whether the addition of a serial CRP levels to usual care for AECOPD is non-inferior to usual care alone, on COPD health status as measured by CCQ

The **secondary objectives** are the effectiveness of the addition of serial CRP levels to usual care in AECOPD patients on:

- General health status as measured by EQ-5D-5L
- Adverse effects of antibiotics
- Cost-effectiveness of individualised CRP-guided antibiotic treatments.

Primary and secondary objectives and outcome measures are listed in Appendix 5.

We hypothesise that:

- (i) antibiotic duration (defined as 'the number of days of antibiotic treatment') in 28 days among AECOPD patients will be significantly lower for CRP-guided antibiotic treatment (including prescription and discontinuation) than usual care
- (ii) COPD health status as measured by the Clinical COPD Questionnaire (CCQ) has no statistically significant difference between two groups;

- (iii) general health status of AECOPD patients as measured by EQ-5D-5L will not be significantly different between the two groups
- (iv) adverse effects of antibiotic treatment in AECOPD patients will not be significantly different between the two groups
- (v) CRP-guided antibiotic treatment will be more cost-effective than usual care

6. Study design

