6.1 Design

Patient-level, multi-centre, single-blind, open-label, randomized, combined superiority (antibiotic duration) and non-inferiority (COPD health status) trial.

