Trained physicians and nurses will help with patient recruitment and data collection in the busy emergency departments.

Baseline subject characteristics will be reported using descriptive statistics such as percentage, medians, and interquartile ranges. COPD-related health status, general health status, and duration of antibiotics use will be compared among groups by Fisher exact tests. Adverse effects and number of events in the intervention group compared to control group will be noted and compared by Chi squared tests.

To estimate the between-group difference on primary outcome of antibiotic duration, two sample T test will be used to the analysis. The other continuous variables including the co-primary outcome (CCQ score) and secondary outcome (EQ-5D) will be analyzed in the same manner.

Fisher 's Exact test will be used to make group comparison for categorical variables such as COPD Severity (GOLD grading), COPD exacerbation severity (Anthonisen criteria) and microbiological pathogen. All available data will be summarized descriptively by tables and figures. All analyses will be performed using Stata software (version 16 or updated version) and considered significant at p<0.05.

For missing data handling, multiple imputation methods will be used to assess the sensitivity of primary outcome results to missing data. Assuming at random, generalised linear models will used for the multiple imputations.

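### Hypotheses (iii) and (iv) can be met only by a non-significant difference test, which does not show that EQ-5D or antibiotic adverse effects are similar

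*Combined protocol and SAP*

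**What the plan says.** Section 5.2 lists the hypotheses to be tested. Hypothesis (iii) is that "general health status of AECOPD patients as measured by EQ-5D-5L will not be significantly different between the two groups". Hypothesis (iv) is that "adverse effects of antibiotic treatment in AECOPD patients will not be significantly different between the two groups". Hypothesis (ii), on the co-primary CCQ, is worded alike: the score "has no statistically significant difference between two groups".

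Section 9 supplies the tests. For adverse effects: "Adverse effects and number of events in the intervention group compared to control group will be noted and compared by Chi squared tests". The t-test described for antibiotic duration is extended to EQ-5D: the "secondary outcome (EQ-5D) will be analyzed in the same manner". The same section, like the Study Summary, also assigns Fisher's exact test to general health status. All analyses are "considered significant at p<0.05".

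Section 6.1 describes a "combined superiority (antibiotic duration) and non-inferiority (COPD health status) trial". Non-inferiority is therefore declared for CCQ alone. The available text gives no margin, equivalence test, confidence-interval rule or power figure for EQ-5D or adverse effects.

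**The concern.** A hypothesis that two groups will not differ significantly is met whenever the difference test returns p≥0.05. That result is compatible with no difference, with a moderate difference the trial was too small to detect, and with data too noisy or incomplete to tell. The noisier the data, the easier the hypothesis is to meet.

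What is at stake is what the trial may say about two secondary outcomes. A moderate rise or a moderate fall in antibiotic adverse effects, or a moderate shift in EQ-5D, could be written up as confirming the hypothesis. The risk is not remote, because the background already makes this step: the part on the team's own work reports no differences in antibiotic-related adverse events in an earlier primary-care CRP trial, then counts adverse events among the outcomes for which non-inferiority has been shown.

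**Working it through.** **Inputs from the documents.** Total N = 1,184 (Study Summary); allocation 1:1 (section 6.6.2), so n = 592 per arm; significance level 0.05 (section 9). Sidedness is not stated; two-sided is assumed.

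**Assumed inputs.** Adverse-effect rates of 5% and 10% in the arm with the lower rate; EQ-5D SD of 0.20 to 0.30; data loss of 0% or 20% (592 or 474 per arm). The documents give none of these. They also give no power figure for these two outcomes, so there is no plan figure to reproduce.

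**Step 1: power for adverse effects.** For rates p0 and p1 with mean p̄,

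z = [|p1 − p0| − 1.96·√(2p̄(1−p̄)/n)] / √(p0(1−p0)/n + p1(1−p1)/n), and power = Φ(z).

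With n = 592:

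| Rates | Calculation of z | Power | Chance of p≥0.05 |
|---|---|---|---|
| 10% vs 13.7% | (0.0370 − 0.0368)/0.0188 = 0.01 | 50% | 50% |
| 10% vs 15.4% | (0.0540 − 0.0379)/0.0193 = 0.83 | 80% | 20% |
| 5% vs 7.8% | (0.0280 − 0.0279)/0.0142 = 0.01 | 50% | 50% |
| 5% vs 9.1% | (0.0410 − 0.0292)/0.0148 = 0.80 | 79% | 21% |
| 5% vs 10% | (0.0500 − 0.0300)/0.0152 = 1.31 | 91% | about 10% |

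The formula is symmetric, so the figures are the same whichever arm has the higher rate. With 474 per arm, the two 50% figures fall to 42%, and 5% vs 10% falls to 83%.

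**Step 2: EQ-5D.** The difference detectable with 80% power is 2.802 × SD × √(2/592) = 0.163 × SD. This is 0.033 at SD 0.20, 0.041 at SD 0.25 and 0.049 at SD 0.30. A true difference of 0.03 would be non-significant 27% to 60% of the time across that SD range; a difference of 0.05, only 1% to 18%.

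**Step 3: what a non-significant result can hide.** Suppose 30 of 592 patients (5.1%) in one arm and 46 of 592 (7.8%) in the other have an adverse effect. The difference is 2.7 points and the pooled rate is 76/1,184 = 6.4%. The pooled standard error is √(2 × 0.0642 × 0.9358/592) = 0.01425, so z = 0.0270/0.01425 = 1.90 and p = 0.058. Hypothesis (iv) is met. The unpooled standard error is 0.01422, so the 95% interval is 2.7 ± 1.96 × 1.42, or −0.1 to 5.5 points. The p-value alone would let the report say there was no significant difference; the interval shows that a gap of up to 5.5 points is not excluded.

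**The case against.** The strongest reply is that section 5.2 states expectations, not a decision rule. A reader might infer that the plan commits to reporting p≥0.05 as proof of no difference, or that an important harm would be reported as confirmation. No section says so, and those readings go too far. For EQ-5D, section 9 even speaks of estimating the between-group difference, so part of the estimation is already intended. This stands as a limit on the claim. It does not remove the problem, because no interval or margin is specified and non-significance remains the only result that satisfies the hypotheses.

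A second reply is that only moderate differences escape, and that these are secondary outcomes. Both are true; the figures above show that a doubling from 5% would usually be found.

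Two further readings are tempting but unsupported. One is that (iv) contradicts the trial's rationale and should predict fewer adverse effects. The background says only that inappropriate antibiotic use may raise the risk of adverse events, and the primary-care trial it cites found no differences in antibiotic-related adverse events although antibiotic use was 57.0% against 77.4%. A neutral (iv) is consistent with that evidence. The other is that (iii) and (iv) carry the word safely in the study aim. The safeguard named in that aim is COPD-related health status, measured by the co-primary CCQ. Serious adverse events are covered in section 8, and pneumonia and hospitalisations in Appendix 5.

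**Conclusion.** The point holds as a flaw in how two secondary hypotheses are framed and tested. As written, (iii) and (iv) can be met only by failing to find a difference, and the plan gives no means of judging similarity. At 592 per arm the exposure is to moderate differences: about 3 to 4 percentage points in adverse effects are missed half the time, and EQ-5D differences under 0.033 to 0.049 have less than 80% power. Loss of data widens this. The figures rest on assumed rates, SDs and a two-sided test; the logical point does not. The error can run in either direction, and a missed reduction in antibiotic adverse effects is as much a possibility as a missed increase. The primary analysis and the sample size are unaffected. The same wording in hypothesis (ii) matters more, because it sits on a co-primary outcome and is at odds with the declared non-inferiority objective.

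**What to change.** Restate (iii) and (iv) as estimation objectives. Report the EQ-5D mean difference and the adverse-effect risk difference between arms, each with a 95% confidence interval, and say in section 9 that no conclusion of similarity will be drawn from p≥0.05. Remove the conflicting assignment of Fisher's exact test to general health status. Do not impose a direction on (iv). Reword hypothesis (ii) so that it states the non-inferiority hypothesis already declared for CCQ.

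This costs nothing in patients, visits or data: it changes wording and adds intervals computed from data already planned.

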6.1 Design

Patient-level, multi-centre, single-blind, open-label, randomized, combined superiority (antibiotic duration) and non-inferiority (COPD health status) trial.

6.2 Study sites

Eligible patients will be recruited via the A&E and relevant departments (e. g. medical wards) of 8 hospitals in 5 hospital clusters in Hong Kong.

6.3 Subjects recruitment

Eligible patients will be recruited via the A&E of 8 hospitals in 5 hospital clusters in Hong Kong. Patients will be screened on arrival in A&E for inclusion and exclusion criteria. Delegated trained personnel will explain the study to the potential subjects and obtain their written consent before joining the study.

6.4 Selection of Subjects

6.4.1 The inclusion criterion:

The inclusion criteria are ALL of the below:

- Being diagnosed with active AECOPD (AECOPD is defined as an event in the natural course of a disease characterized by a change in baseline dyspnoea, cough, and/or sputum that is beyond the normal day-to-day variations with acute onset, which may warrant a change in regular medication in patients with underlying COPD).⁵
- 2. Known COPD in their medical records.
- 3. Age 40 years or older.
- 4. Able to provide informed consent in Cantonese, Mandarin, or English
- 5. Able to complete the questionnaires during the study period (i.e. 6 months after randomisation)

6.4.2 The exclusion criteria:

Patients will be excluded if any ONE of the following are present:

1. Pre-treatment with systemic corticosteroids for the present exacerbation.

- 2. Pre-treatment with any antibiotics for the present exacerbation, any concurrent infection or prophylaxis.
- 3. Known clinical stroke in past 6 months
- 4. Patients with high suspicion of active AECOPD mimics:
 - 1) Pneumonia
 - 2) Congestive heart failure
 - 3) Bronchiectasis
 - 4) Pulmonary embolism
 - 5) Pneumothorax
 - 6) Atrial fibrillation / flutter
- 5. Lung comorbidities:
 - 1) Cystic fibrosis
 - 2) Tuberculosis
 - 3) Unresolved lung malignancy
- 6. Progression or new radiographic abnormalities on the chest X-ray.
- 7. Immunodeficiency disorders such as AIDS, humoral immune defect, ciliary dysfunction etc., and the use of immunosuppressive drugs for more than 28 days.
- 8. Active inflammatory condition (e.g. flare up of rheumatoid arthritis, gout or polymyalgia rheumatica) or concurrent infection at another site (e.g. UTI, cellulitis) that is likely to produce a systemic response
- 9. Currently pregnant
- 10. NEWS2 score¹⁹ of \geq 3

6.5 Intervention

This is a two-arm, open, single-blind, single-centred, individually randomised controlled trial involving emergency physicians in ED. This trial will evaluate the addition of serial CRP levels to usual care to guide antibiotics management decisions for patients presenting in ED with AECOPD, which is the first in the world. Patients presenting with AECOPD will be randomised to clinical management based on usual care alone or usual care with the addition of a serial CRP levels.

Control arm

Patients in the control arm will be treated with usual care (GOLD initiative). No CRP would be measured.

Intervention arm

Training in CRP interpretation will help to guide decisions about the use of antibiotic treatment for AECOPD. All serum CRP tests will be conducted by the local pathology laboratory in each

participating hospital. These laboratories have been accredited by Hong Kong Laboratory Accreditation Scheme (HOKLAS) based on ISO standards.

The attending doctor will use the CRP level to inform their decision to continue antibiotics around 3 hours from blood taking. These doctors will be provided pre-study training on CRP interpretation.

Every day from randomization, serum CRP testing will be encouraged to take. Once CRP has declined to <5mg/dL and the patient has remained afebrile for past 48 hours, antibiotic treatment will be reviewed for discontinuation. Otherwise, antibiotic treatment will be continued. A switch on the administration route, or a change of antibiotics due to adverse effect, allergy, or suggestion from culture result, is permitted according to in-patient physician's decisions. CRP will continue to be monitored daily upon discharge from that hospital (up to 28 days).

